14.1.4 Closed to Follow-Up

The study is considered Closed to Follow-Up when all protocol-defined follow-up procedures have been completed for all patients who have not been removed from the study for other reasons. That is, there are no outstanding follow-up procedures to be performed as mandated by the protocol.

CTEP does **not** need to be notified of a status change to “Closed to Follow Up.”

14.1.5 Complete

Study is considered Complete if it has been at least thirty (30) days since the last patient follow-up evaluation.

A citation to a final study report (manuscript, meeting abstract, etc.) is required with the submission of the Protocol Status Update Form to CTEP PIO.

RESPONSE CRITERIA FOR ALTERING NATURAL HISTORY OF MDS**

Category	Response criteria (responses must last at least 4 weeks)
Complete remission	Bone marrow: $\leq 5\%$ myeloblasts with normal maturation of all cell lines* Persistent dysplasia will be noted*† Peripheral blood‡ Hgb ≥ 11 g/dL Platelets $\geq 100 \times 10^9/L$ Neutrophils $\geq 1.0 \times 10^9/L^†$ Blasts 0%
Partial remission	All CR criteria if abnormal before treatment except: Bone marrow blasts decreased by $\geq 50\%$ over pretreatment but still $> 5\%$ Cellularity and morphology not relevant
Marrow CR [†]	Bone marrow: $\leq 5\%$ myeloblasts and decrease by $\geq 50\%$ over pretreatment [†] Peripheral blood: if HI responses, they will be noted in addition to marrow CR [†]
Stable disease	Failure to achieve at least PR, but no evidence of progression for > 8 wks
Failure	Death during treatment or disease progression characterized by worsening of cytopenias, increase in percentage of bone marrow blasts, or progression to a more advanced MDS FAB subtype than pretreatment
Relapse after CR or PR	At least 1 of the following: Return to pretreatment bone marrow blast percentage Decrement of $\geq 50\%$ from maximum remission/response levels in I granulocytes or platelets Reduction in Hgb concentration by ≥ 1.5 g/dL or transfusion dependence
Cytogenetic response	Complete Disappearance of the chromosomal abnormality without appearance of new ones Partial At least 50% reduction of the chromosomal abnormality For patients with:
Disease progression	

Less than 5% blasts: $\geq 50\%$ increase in blasts to $> 5\%$ blasts
5%-10% blasts: $\geq 50\%$ increase to $> 10\%$ blasts
10%-20% blasts: $\geq 50\%$ increase to $> 20\%$ blasts
20%-30% blasts: $\geq 50\%$ increase to $> 30\%$ blasts

Any of the following:

At least 50% decrement from maximum remission/response in granulocytes or platelets
Reduction in Hgb by ≥ 2 g/dL
Transfusion dependency

Survival	Endpoints: Overall: death from any cause Event free: failure or death from any cause PFS: disease progression or death from MDS DFS: time to relapse Cause-specific death: death related to MDS
----------	--

To convert hemoglobin from grams per deciliter to grams per liter, multiply grams per deciliter by 10.

MDS indicates myelodysplastic syndromes; Hgb, hemoglobin; CR, complete remission; HI, hematologic improvement; PR, partial remission; FAB, French-American-British; AML, acute myeloid leukemia; PFS, progression-free survival; DFS, disease-free survival.

* Dysplastic changes should consider the normal range of dysplastic changes (modification).

† Modification to IWG response criteria.

‡ In some circumstances, protocol therapy may require the initiation of further treatment (eg, consolidation, maintenance) before the 4-week period. Such patients can be included in the response category into which they fit at the time the therapy is started. Transient cytopenias during repeated chemotherapy courses should not be considered as interrupting durability of response, as long as they recover to the improved counts of the previous course.

**APPENDIX A2 MODIFIED INTERNATIONAL WORKING GROUP (IWG)-2006
RESPONSE CRITERIA FOR HEMATOLOGIC IMPROVEMENT**

Hematologic improvement*	Response criteria (responses must last at least 8 wk)[†]
Erythroid response (pretreatment, < 11 g/dL)	Hgb increase by ≥ 1.5 g/dL Relevant reduction of units of RBC transfusions by an absolute number of at least 4 RBC transfusions/8 wk compared with the pretreatment transfusion number in the previous 8 wk. Only RBC transfusions given for a Hgb of ≤ 9.0 g/dL pretreatment will count in the RBC transfusion response evaluation [†]
Platelet response (pretreatment, $< 100 \times 10^9/L$)	Absolute increase of $\geq 30 \times 10^9/L$ for patients starting with $> 20 \times 10^9/L$ platelets Increase from $< 20 \times 10^9/L$ to $> 20 \times 10^9/L$ and by at least 100% [†]
Neutrophil response (pretreatment, $< 1.0 \times 10^9/L$)	At least 100% increase and an absolute increase $> 0.5 \times 10^9/L$ [†]
Progression or relapse after HI [‡]	At least 1 of the following: At least 50% decrement from maximum response levels in granulocytes or platelets Reduction in Hgb by ≥ 1.5 g/dL Transfusion dependence

Deletions to the IWG response criteria are not shown.

To convert hemoglobin levels from grams per deciliter to grams per liter, multiply grams per deciliter by 10.

Hgb indicates hemoglobin; RBC: red blood cell; HI: hematologic improvement.

* Pretreatment counts averages of at least 2 measurements (not influenced by transfusions) ≥ 1 week apart (modification).

[†] Modification to IWG response criteria.

[‡] In the absence of another explanation, such as acute infection, repeated courses of chemotherapy (modification), gastrointestinal bleeding, hemolysis, and so forth. It is recommended that the 2 kinds of erythroid and platelet responses be reported overall as well as by the individual response pattern.

APPENDIX A3 INTERNATIONAL WORKING GROUP ACUTE MYELOID LEUKEMIA RESPONSE CRITERIA

Response Criterion	Time of Assessment	Neutrophils (μ L)	Platelets (μ L)	Bone Marrow Blasts (%)	Other
Early treatment assessment	7-10 days after therapy	NA	NA	< 5	
Morphologic leukemia-free State	Varies by protocol	NA	NA	< 5	Flow cytometry EMD
Morphologic CR	Varies by protocol	> 1,000	> 100,000	< 5	Transfusion EMD
Cytogenetic CR	Varies by protocol	> 1,000	> 100,000	< 5	Cytogenetics—normal, EMD
Molecular CR	Varies by protocol	> 1,000	> 100,000	< 5	Molecular—negative, EMD
Partial Remission	Varies by protocol	> 1,000	> 100,000	> 50 or decrease to 5-25	Blasts < 5% if Auer rod positive

Table 11: Hematologic Response According to IWG Criteria for AML

AML = acute myelogenous leukemia; CR = complete remission; EMD = extramedullary disease; onal Working Group; NA = not applicable ([Cheson, 2003](#)).

**APPENDIX B INTERNATIONAL PROGNOSTIC SCORING SYSTEM (IPSS)
FOR MYELODYSPLASTIC SYNDROME**

PROGNOSTIC VARIABLE	SCORE VALUES				
	0	0.5	1.0	1.5	2.0
Marrow Blasts (%)†	<5	5-10	—	11-20	21-30
Karyotype*	Good	Intermediate	Poor		
Cytopenias**	0/1	2/3			

†Patients with 21-30% blasts are considered as MDS or AML (WHO)

*Cytogenetics: Good = normal, -Y alone, del(5q) alone, del(20q) alone, Poor = complex (≥ 3 abnormalities) or chromosome 7 anomalies; Intermediate = other abnormalities

**Cytopenias: neutrophil count < 1800/ μ l, platelets < 100,000, Hb < 10 g/dL.

Risk category (% IPSS pop.)	Overall score	Median survival (yr)	25% AML progression (yr)
LOW (33)	0	5.7	9.4
INT-1 (38)	0.5-1.0	3.5	3.3
INT-2 (22)	1.5-2.0	1.1	1.1
HIGH (7)	>2.5	0.4	0.2

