3. PATIENT SELECTION

3.1 Eligibility Criteria

3.1.1 Pathologically confirmed MDS diagnosis (regardless of initial IPSS risk category) or oligoblastic AML with 21-30% BM blasts in whom DNMTi have failed. Patients who have developed AML after DNMTi therapy can be enrolled as long as they have initiated DNMTi therapy while they were in the MDS or oligoblastic AML (20-30% BM blasts) phase and the study chair agrees. Failure of DNMTis is defined as: Failure to achieve a CR, PR or HI after at least 4 cycles of DNMTi or progressed after such therapy.

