11. MEASUREMENT OF EFFECT

Although response is not the primary endpoint of this trial, patients will be assessed for objective response by the standard criteria of modified IWG-2006 guidelines ([Appendix A1](#) and [Appendix A2](#)). Responses in AML patients will be assessed using IWG 2003 criteria ([Appendix A3](#)). In addition to a baseline bone marrow biopsy and scan, bone marrow biopsy will be performed at baseline, after cycles 2 and 4, and before each maintenance dose.

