11.2 Response criteria

Myelodysplastic syndrome (MDS)

Responses for MDS patients will be defined as in the modified IWG-2006 criteria ([Appendix A1](#) and [Appendix A1](#)). These response criteria do not apply to AML as these patients are required to be in full remission by eligibility criteria. Only relapse and survival as measured by PFS and overall survival will be measured to assess response for AML patients. The OS and PFS will be measured for both AML and MDS as described in [Appendix A1](#) and [Appendix A2](#).

Duration of response: The duration of overall response is measured from the time measurement criteria are met for CR or PR (whichever is first recorded) until the first date that recurrent or progressive disease is objectively documented (taking as reference for progressive disease the smallest measurements recorded since the treatment started).

Duration of stable disease: Stable disease is measured from the start of the treatment until the criteria for progression are met.

Chronic Myelomonocytic Leukemia (CMML)

The definitions below are consistent with those detailed by Cheson, et al for MDS⁶¹ except that, as discussed earlier, for disease progression based on BM blast percentage, the patient must exceed 10% absolute BM blast percentage in addition to increasing above 50% of BM blast percentage at baseline to count as disease progression.

Complete response is defined by bone marrow showing <5% myeloblasts with normal trilineage maturation without dysplasia. When erythroid precursors constitute <50% of marrow cells, the blast percentage is based on total nucleated cells; otherwise, the blast percentage is based on non-erythroid compartment. Peripheral blood criteria consist of Hemoglobin \geq 11 gm/dl, ANC \geq 1 x 10⁹/L, Platelets \geq 100 x 10⁹/L, absence of peripheral blood blasts, all in the absence of transfusions and growth factors.

Partial response is defined by all of the above criteria with the exception of bone marrow blasts decreasing by >50% from pretreatment levels and/or achievement of a less advanced MDS FAB classification.

Stable Disease is defined by failure to achieve PR but without progression for at least 2 months.

Progression is defined according to initial blast percentages:

For patients with <5% blasts: \geq 50% increase in blasts to >10%

For patients with 5-10% blasts: \geq 50% increase in blasts to >10%

For patients with >10-20% blasts: \geq 50% increase in blasts to >20%

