13.4 Analysis of Secondary Endpoints

Overall response rate: defined by the International working group 2006 (IWG-2006) criteria for CR, PR, HI ([Appendix A1](#) and [Appendix A2](#)). We will also record PFS and OS for the

MDS. These endpoints will be assessed after cycle 2 and 4 of induction therapy, and every 3 months during follow-up. Bone marrow biopsies will be done at baseline, after 1 cycle and then every 2 cycles, at end of study, and as clinically indicated (e.g. suspicion of progression, decreasing blood counts). We aim to obtain preliminary efficacy data of entinostat in combination with Pembrolizumab (MK-3475) in terms of CR, PR, HI as defined by IWG-2006 and PFS, OS. Rates of CR, PR and HI will be summarized separately by cohort and reported with an exact 95% confidence interval. Median PFS and OS will also be reported with a 95% confidence interval.

The quantitative change in MDSCs (% MDSCs by flow cytometry, QIF score by AQUA) during treatment with the ENT/anti-PD1 combined therapy will be estimated using mixed effects models to take into account the within-patient correlation. Likelihood ratio tests will be performed to confirm if random intercepts and slopes are necessary in the model. The fixed effect for change in MDSCs over time will be evaluated for significance. The variability in the rate of change in MDSCs across patients will also be examined. The association between the clinical outcome and a meaningful reduction in MDSCs, which will be defined after a review of the data, will be assessed with the chi-square test. The quantity of MDSCs at baseline and during treatment as continuous variables can also be compared between responding and non-responding patients using a t-test or Mann-Whitney U-Test, if more appropriate.

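### The AML partial-remission cell in Appendix A3 requires no minimum blast reduction as printed, and the plan contradicts itself on whether such a response counts in ORR

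*Combined protocol and SAP*

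**What the plan says.** Section 11 of the protocol sends AML patients to Appendix A3: "Responses in AML patients will be assessed using IWG 2003 criteria". In the partial-remission row of that table, the marrow-blast cell is "> 50 or decrease to 5-25". The row also sets neutrophils above 1,000 and platelets above 100,000 per µL.

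For MDS, Appendix A1 defines partial remission by a blast decrease of 50% or more from pretreatment, with blasts still above 5%.

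Section 3.1.1 admits "oligoblastic AML with 21-30% BM blasts in whom DNMTi have failed". It also admits later AML: "Patients who have developed AML after DNMTi therapy can be enrolled as long as they have initiated DNMTi therapy" in the MDS or oligoblastic phase and the study chair agrees. No upper blast limit is stated for that second group.

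On the endpoint, Section 13.4 has "Overall response rate: defined by the International working group 2006 (IWG-2006) criteria for CR, PR, HI" and points to Appendices A1 and A2. Section 13.1 does the same. Section 11.2 says of AML: "Only relapse and survival as measured by PFS and overall survival will be measured to assess response for AML patients". Section 13.5.2 assigns every patient a response category, partial response among them, and puts eligible patients into the main response-rate analysis. Under Section 13.2, two responses reject a 1% null response rate.

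**The concern.** The blast cell joins its two limbs with 'or'. Under a column headed as blast percentage, the first limb would make blasts above 50% a partial remission, which cannot be meant. The second limb then stands alone, and a decrease to anywhere in 5–25% is enough on blasts. Much of the oligoblastic entry range already lies inside that interval or just above it.

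The same marrow could therefore face two very different standards according to its label, and Appendix B says that 21–30% blasts may be classed as MDS or AML. A patient at 24% labelled MDS must reach 12% or lower. Labelled AML, 23% meets the blast criterion. A1 also asks for a response lasting at least 4 weeks, while A3 states no duration.

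The stake is the ORR decision. ORR is secondary, but it carries the signal for further study and turns on two patients.

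**Working it through.** **1. The plan's own figures.** Inputs from Section 13.2: N from 21 to 27, rule X ≥ 2, null 1%, alternative 15%, one-sided exact binomial.

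- N=21: alpha = 1 − .99^21 − 21(.01)(.99^20) = 1 − .8097 − .1718 = .0185. Power at 15% = 1 − .85^21 − 21(.15)(.85^20) = .845 (.84496 before rounding).
- N=27: alpha = .0297, power = .928.

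To two decimals these give the stated alpha of .02 to .03 and power of .84 to .93. The plan's figures reproduce.

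**2. Blast change needed.** For baseline b, the second A3 limb needs a fall of b − 25 points if b > 25, and any decrease if b is 21–25. A 50% reduction needs b/2 points.

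| Baseline (%) | A3 as printed, second limb | 50% reduction |
|---|---|---|
| 21 | any decrease | 10.5 points |
| 24 | any decrease | 12 points |
| 25 | any decrease | 12.5 points |
| 26 | 1 point (3.8% relative) | 13 points |
| 28 | 3 points (10.7%) | 14 points |
| 30 | 5 points (16.7%) | 15 points |

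For AML entering above 30%, the A3 limb stays the looser of the two for any baseline below 50%, because b − 25 < b/2 whenever b < 50. At 40%, for example, it needs 15 points against 20.

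**3. Effect on alpha if A3 partial remissions count.** Let k be the number of AML patients and q the probability that one of them is scored a spurious partial remission, meaning that the blast limb and both count limits are all met. The documents give neither, so both are assumptions. The other N − k patients respond at the null 1%. With X ~ Bin(N − k, .01) and Y ~ Bin(k, q), alpha = P(X + Y ≥ 2).

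Worked case, N=21, k=2, q=.05:

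- P(0) = .99^19 × .95² = .7456
- P(1) = 19(.01)(.99^18)(.95²) + .99^19 × 2(.05)(.95) = .1431 + .0785 = .2216
- alpha = 1 − .7456 − .2216 = .0328

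| N | k | q=.05 | q=.10 | q=.20 |
|---|---|---|---|---|
| 21 | 1 | .025 | .033 | .050 |
| 21 | 2 | .033 | .054 | .105 |
| 21 | 5 | .061 | .137 | .327 |
| 27 | 2 | .047 | .071 | .128 |
| 27 | 5 | .079 | .159 | .351 |

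**4. Does an A3 partial remission reach ORR?**

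- For: Section 11 assigns AML patients to A3, and Section 13.5.2 puts all eligible patients into the response-rate analysis.
- Against: Sections 13.1 and 13.4 name only A1 and A2, and Section 11.2 limits AML to relapse, PFS and OS.
- Section 11.2 rests on AML patients being in full remission by eligibility. Section 3.1.1 enrols them with active disease, so that premise fails.
- Appendix B leaves open whether a patient at 21–30% is scored as MDS (A1) or AML (A3).

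The documents support both answers.

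**The case against.** **The cell may be damaged.** Other parts of the A3 table are plainly broken in the available text, and the 50 has lost, or never had, a percent sign and the word for reduction. The intended rule may be a 50% decrease to 5–25%. This stands as a reason to check the source table before anything else. It does not dispose of the point: 'or' is a whole word rather than a dropped symbol, the row's count cells are legible, and the cell is not a usable rule on any reading.

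**A blast change alone is not a response.** A reader might infer that a fall of 1–5 points supplies a partial remission. It does not. The row also needs both blood-count thresholds, and Section 5.2 describes severe cytopenias as common in this population. This stands and limits how many patients are affected. It does not remove the problem, because eligibility sets no blood-count limits and a patient already above both thresholds has only the blast limb to meet. That feature is not peculiar to A3: A1 applies its count criteria only when abnormal at the start ("All CR criteria if abnormal before treatment except"). A1, however, keeps the 50% blast reduction as a separate hurdle.

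**No clear route into ORR.** Sections 13.1 and 13.4 never name A3, and Section 11.2 would exclude AML response altogether. This stands to the extent that one cannot say A3 partial remissions will count. Nor can one say they will not.

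**The size is not known.** A reader might take .18 as the inflated error rate, since 1 − .99^20 = .182 is the chance of rejecting the null at N=21 once one spurious partial remission has been counted (.230 at N=27). That probability is conditional on the spurious response having occurred. It is not the design's type I error and should not be set beside .0185 as if it were. The documents also give no figure for repeat-marrow variation, so q can only be assumed.

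**Conclusion.** The point holds in limited form. As printed, the A3 partial-remission blast criterion is unusable in one limb and sets no minimum reduction in the other, so oligoblastic AML can meet it with a trivial change. This matters only for patients who also meet both count thresholds, and only if A3 responses enter ORR, which the plan leaves contradictory.

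Under the assumed k and q, alpha at N=21 lies between .033 and .105 with 2 AML patients and between .061 and .327 with 5. These figures illustrate sensitivity and do not estimate the trial's error rate. A single AML patient at q=.05 gives .025, still within the stated range, so the harm depends on how many AML patients enrol and how often all three conditions are met by chance.

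A reader might also infer that all AML in the trial enters at 21–30%. That range applies to oligoblastic AML only. AML that developed after DNMTi has no stated ceiling, and for it the gap between the two standards narrows as baseline blasts approach 50%.

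The correction should be made before responses are scored. The primary MTD endpoint is not affected.

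**What to change.** 1. Check the A3 partial-remission cell against the source table.
2. Restate it as a decrease of at least 50% from pretreatment, to 5–25% blasts, with both conditions required. This is the reduction A1 already uses.
3. Reconcile Sections 11, 11.2, 13.1, 13.4 and 13.5.2 so that one statement says which criteria AML patients use for ORR, and whether a patient with 21–30% blasts is scored under A1 or A3. Remove the full-remission premise from Section 11.2.
4. List AML responders separately, with baseline and best blast counts, so that readers can see how much of the ORR rests on them.

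The cost is one table cell, a short clarification across those sections and one listing. The downside is that a few marginal AML changes no longer count as partial remission. Section 5.1 continues treatment for stable disease as well as response, so rescoring such a patient as stable disease would not alter that continuation rule.

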APPENDIX C PERFORMANCE STATUS BY ECOG GRADING CRITERIA

ECOG Performance Status Scale	
Grade	Descriptions
0	Normal activity. Fully active, able to carry on all pre-disease performance without restriction.
1	Symptoms, but ambulatory. Restricted in physically strenuous activity, but ambulatory and able to carry out work of a light or sedentary nature (e.g., light housework, office work).
2	In bed <50% of the time. Ambulatory and capable of all self-care, but unable to carry out any work activities. Up and about more than 50% of waking hours.
3	In bed >50% of the time. Capable of only limited self-care, confined to bed or chair more than 50% of waking hours.
4	100% bedridden. Completely disabled. Cannot carry on any self-care. Totally confined to bed or chair.
5	Dead.

**APPENDIX D PROTOCOL FOR MONONUCLEAR CELLS ISOLATION
(FICOLL HYPAQUE):**

1. Resuspend bone marrow aspirates with PBS (1:1)
2. Gently layer the diluted suspension over 5 ml of F/H in a 15 ml conical tube. You can load up to 10 mL however limiting this to 9 ml or less reduced the chances of contacting the cap.
3. Spin at 400g (1200rpm) for 30 minutes at Room Temp (22-24C). Do not set the brake on the centrifuge.
4. Carefully remove the tube from the centrifuge. Using a glass pipette carefully remove the interface (white) containing the MNC. This should take less than 2 ml per 15 ml conical (1 ml if you are careful not to disturb the layer).
5. Transfer the cells to a fresh 15 ml conical tube and add PBS up to 10 ml (at least a 1:4 dilution). Mix well then spin at 400g (1200rpm) for 10 minutes at Room Temp (22-24C).
6. Carefully aspirate the supernatant and resuspend the cells in 10 ml of PBS. Mix well then spin at 400g (1200rpm) for 10 minutes at Room Temp (22-24C).
7. Carefully aspirate the supernatant and resuspend the cells in 10 ml of PBS. Mix well then spin at 400g (1200rpm) for 10 minutes at Room Temp (22-24C).
8. Resuspend the cell in a small volume of PBS or culture medium and count after mixing well.
9. To cryopreserve the cells (minimum of 4 vials not to exceed 2x10⁷/vial).
 - a. The final concentration will usually be 40% Human Serum, 10% DMSO:
 1. The easiest method is to dilute the cells to a twice the final concentration in PBS and to add an equivalent volume of cells (500 ul) to a 2X freezing medium (80% Serum, 20% DMSO) prechilled to 4C.
 2. Transfer right away to a labeled cryovial and use a controlled rate device to drop the temperature to -80C prior to transfer to Liquid Nitrogen. The rate is usually ideal at -1C per minute for PBMC.

Important considerations:

1. All work should be done using standard BSL2 procedures (blood and body fluid precautions).
2. Maintain a clean workspace and use a containment laminar airflow hood when possible.
3. Minimize the chance of contamination.
4. Work quickly but methodically.
5. Keep tubes closed as much as possible and work quickly.
6. Change gloves frequently and maintain situational awareness of contact surfaces.

